## **9) Statistics\***

Statistical analyses will be performed using SPSS version 21 (IBM Corporation, Armonk, NY). Parametric data are reported as  $M \pm SD$  and nonparametric data are reported as median (interquartile range). Missing values for continuous variables are handled by applying imputation methods before calculating their statistics. The study population will be stratified into two halves based on the primary outcome of change from baseline SOFA and/or ICH DC. Those with the fastest rate of recovery are compared to those with the slowest rate of recovery. We expect that AT3 will correlate with rate of recovery and/or with one or more of the secondary outcomes. The demographics and physiologic variables in the fastest and slowest groups are compared using a t test or Mann-Whitney U-test, as appropriate. Categorical variables are compared using a  $\chi^2$  or Fisher's exact test, as appropriate. Statistical significance is determined at  $p < 0.05$ . Then multivariate models will be evaluated for predicting the primary or secondary outcomes, using various performance metrics, such as area under the receiver operating characteristic curve, sensitivity and specificity, positive predictive value, and negative predictive value, as we have described in multiple previous studies. In addition, propensity scores will be assigned for each patient based on a 1:1 fixed ratio nearest neighbor matching was performed to compare those with fastest or slowest recovery. A 1:1 fixed ratio nearest neighbor matching is performed to minimize bias without sacrificing power, as we have described in multiple previous studies.

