**7) Study Endpoints\***

The Primary endpoint is change from baseline in the ISTH DIC Score to Day 9.

The Secondary endpoints include change from baseline D-dimers, Fibrinogen & Prothrombin time, length of hospital stay (days), mortality (%), and Pulmonary function (including Time (days) to mechanical ventilation and/or ECMO Duration (days) of new ventilator or extracorporeal membrane oxygenation (ECMO) use, Change from baseline SOFA and SOFA Respiratory sub-score, Number of venous thromboembolisms, Number of major bleeding events

Subjects discharged prior to completion of intervention would be classified as having a successful outcome. We anticipate that all cause morbidity will occur in 10-20% of the COVID study population, despite standard of care. We anticipate that these patients will be deficient in endogenous AT3.

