**8) Procedures Involved\***

Any member of the study team will discuss potential subjects with the clinical team for appropriate pursuit of informed consent and screening for eligibility.

75 eligible subjects, after consent, will have laboratory blood tests for further screening.

25 of those subjects with endogenous **AT3  $\geq$  100%** will continue with SOC.

50 of those subjects with endogenous **AT3 < 100%** will be will be randomly assigned to begin **SOC plus treatment with exogenous AT3 supplementation or only SOC** treatment. The randomization schedule will be established by a member of the study team that is not involved in the informed consent process.

They will all be followed up for laboratory blood tests, study endpoints and adverse events. If they do not meet entry criteria they will be excluded from the study.

[figure not shown]
Consented subjects will be scored according to The International Society of Thrombosis and Haemostasis Disseminated Intravascular Coagulation scale (ISTH DIC) on study visit days 1, 3, 5, 7, 9 and 11.

The SOFA score will be performed only when the parameter is obtained clinically and monitored for changes in patient status on study visit days 1, 3, 5, 7, 9 and 11. Each organ system is assigned a point value from 0 (normal) to 4 (high degree of dysfunction/failure). It will be calculated on admission and Day 11 using the worst parameters measured during the study visit day. If a parameter is not obtained clinically it will be voided for research purposes.

UM IRB# 20201048

AT3 in COVID-19  
January 24, 2022, Version 6.2

After enrollment and each 48h period (+/- 12 hours) thereafter, blood samples are collected and assayed for routine clinical coagulation and inflammation markers, including AT3 activity, D-Dimer, anti-Xa, fibrinogen, and prothrombin time until Day 11.

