### Appendix C

The Secondary endpoint measurements:

- a. D-dimer level change from baseline to Day 9 in mcg/mL FEU or DDU,
- b. Fibrinogen level change from baseline to Day 9 in mg/dL
- c. Prothrombin time change from baseline to Day 9 in seconds
- d. Length of hospital stay in days,
- e. Mortality (%) of overall and between groups,
- f. Pulmonary function
  - a. Time (days) to mechanical ventilation and/or
  - b. ECMO Duration (days) or extracorporeal membrane oxygenation (ECMO) use,
- g. SOFA score change from baseline to Day 9 and
- h. SOFA Respiratory sub-score change from baseline to Day 9,
- i. Number of venous thromboembolisms from admission to hospital discharge,
- j. Number of major bleeding events from admission to hospital discharge

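### Section 9 lets SOFA and/or a DIC measure serve as the primary outcome that forms the compared halves, but Section 7 names ISTH DIC change to Day 9 alone and makes SOFA secondary

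*Combined protocol and SAP*

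**What the plan says.** Section 7 (Study Endpoints) is explicit: "The Primary endpoint is change from baseline in the ISTH DIC Score to Day 9". Its list of secondary endpoints includes "Change from baseline SOFA and SOFA Respiratory sub-score". Appendix C, which is devoted to the secondary endpoints, agrees and adds a day: "SOFA score change from baseline to Day 9".

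Section 9 (Statistics) describes the primary outcome differently: "The study population will be stratified into two halves based on the primary outcome of change from baseline SOFA and/or ICH DC". The next step is a comparison of the two halves: "Those with the fastest rate of recovery are compared to those with the slowest rate of recovery". Demographic and physiologic variables are tested between the halves at p < 0.05, and 1:1 nearest-neighbour propensity matching is applied to the same contrast. Section 9 also says that "multivariate models will be evaluated for predicting the primary or secondary outcomes".

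On timing, Section 8 scores the "Disseminated Intravascular Coagulation scale (ISTH DIC) on study visit days 1, 3, 5, 7, 9 and 11". For SOFA, Section 8 says two things. It is to be followed on those same six days where the parameters are obtained clinically, and "It will be calculated on admission and Day 11 using the worst parameters measured during the study visit day". The flowsheet in Appendix B marks ISTH DIC at every visit and SOFA at Day 1 and Day 11 only.

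**The concern.** One document describes its primary outcome in two ways. The endpoint section has a single instrument. The statistics section, which an analyst would carry out, has a secondary instrument joined by and/or to something that is probably the primary one. No passage sets an order of precedence or says how the and/or is to be resolved.

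The choice is not cosmetic. In Section 9 this outcome decides which patients belong to the fastest and slowest halves, and the group tests and the matching rest on that division. Two analysts who both follow the plan could compare different sets of patients and report different associations between AT3 and recovery. If the choice is made only after the data are in, a reader cannot tell whether it was influenced by the results.

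**Working it through.** **The passages side by side.** The plan states no figure that depends on this point, so the check is mainly one of text.

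| Place | Instrument | Status | Day |
|---|---|---|---|
| Section 7 | ISTH DIC change | primary | 9 |
| Section 7 | SOFA change | secondary | not given |
| Appendix C | SOFA change | secondary | 9 |
| Section 9 | SOFA and/or ICH DC | called primary | not given |

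ICH DC is defined nowhere. Reading it as ISTH DIC, Section 9 still allows three bases for the halves: SOFA alone, DIC alone, or both. Only DIC alone agrees with Section 7. The other two let a secondary endpoint help define the primary grouping.

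**Illustration: how many patients could change half.** Inputs: n = 75 (Section 4) and an assumed correlation ρ between the SOFA and DIC changes. For two median splits of bivariate normal variables, the expected number placed in different halves is 75 × arccos(ρ)/π.

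- ρ = 0: 75 × 0.500 = 37.5
- ρ = 0.5: 75 × 0.333 = 25.0
- ρ = 0.8: 75 × 0.205 = 15.4
- ρ = 0.9: 75 × 0.144 = 10.8

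A simulation with whole-number scores used assumed SDs of 0.5 to 1.8 for DIC change and 2.5 for SOFA change, with three ways of handling ties. It gave 31.9–37.5 patients at ρ = 0, 24.4–28.6 at 0.5 and 15.8–27.1 at 0.8. Platelet count enters both scores (Appendix A), so the zero-correlation row is a poor guide.

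**Illustration: error rate for one null variable.** Suppose a variable unrelated to recovery is tested between halves at 0.05, and either split could be used. With independent tests the chance of at least one false positive is 1 − 0.95² = 0.0975. In the simulation (ρ from 0 to 0.8) it was 0.087–0.099, against 0.045–0.053 with the DIC split alone.

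**Ties under the Section 7 endpoint.** From Appendix A the DIC score runs from 0 to 2 + 1 + 2 + 3 = 8 in whole numbers; SOFA runs from 0 to 6 × 4 = 24. Take an assumed DIC change with mean −0.3 and SD 1.0, rounded. The expected number tied at the median value of 0 is about 75 × [Φ(0.8) − Φ(−0.2)] = 75 × 0.367 = 27.6; the simulation gave 28.0. For SDs of 0.5, 1.5 and 1.8 it gave 45.1, 20.0 and 17.1, against 12.8 for SOFA. Moving all tied patients from the fast to the slow half would thus shift about 17 to 45 patients, even with DIC and Day 9 fixed. Since 75 is odd, exact halves are impossible in any case (37 and 38).

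**The case against.** The best defence is that the text leans one way. Section 7 is where endpoints are defined, Appendix C lists SOFA as secondary, and Appendix B schedules ISTH DIC but not SOFA on Day 9. Only Section 9 departs, in a phrase that is visibly garbled. This is a pilot, and the halves are used to compare patient characteristics, not the randomised arms. Most of this stands, and it makes the repair easy. It does not remove the conflict: a typing slip may explain ICH DC, but it does not explain SOFA joined by and/or.

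A reader might draw stronger conclusions that the documents do not support:

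- **Five rival definitions of the primary outcome**, because DIC is scored on five post-baseline days and Section 9 names none. Section 9 refers to the primary outcome and Section 7 gives its day; not repeating the day is no contradiction. The five days are scoring visits.
- **The wording decides which multivariable model is primary.** Section 9 designates no model as primary and treats primary and secondary outcomes alike.
- **SOFA is never available on Day 9.** Section 8 also has it followed on Day 9 when obtained clinically. The text is mixed rather than plainly opposed to Appendix C.
- **The trial intends to choose its outcome late.** Nothing in the text shows this; careless drafting is at least as likely.

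It is also fair to say that naming one endpoint does not by itself make the halves reproducible. The many ties at the DIC median and the undefined term rate of recovery would still leave room, so the repair has to cover both.

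**Conclusion.** The point holds. As written, Section 9 contradicts Section 7 and Appendix C on what the primary outcome is, and no passage settles which applies. Because the conflict concerns the primary outcome itself and the grouping on which Section 9 rests, it should be resolved before any analysis. That conclusion depends on the text alone.

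The size is not known. The counts of patients moved (about 11 to 37.5 of 75 by the closed form, for ρ from 0.9 down to 0) and the roughly 9–10% false-positive chance follow wholly from assumed correlations, means and SDs; the documents give none. A reader might take the 9–10% as the error rate of a treatment comparison or of the primary result. It is neither: it concerns one unrelated variable compared between recovery halves. The absence of a primary comparison between the randomised arms is a separate matter.

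**What to change.** In Section 9:

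1. Replace SOFA and/or ICH DC with the Section 7 endpoint: ISTH DIC score, change from baseline to Day 9, with a cross-reference to Section 7.
2. State that SOFA change is secondary and does not define the halves.
3. State that rate of recovery means this same change to Day 9.
4. Give one fixed rule for patients tied at the median, written before the data are examined.

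Separately, reconcile the SOFA time point across Appendix C (Day 9), Appendix B (Day 1 and Day 11 only) and Section 8 (followed on Days 1, 3, 5, 7, 9 and 11, yet calculated on admission and Day 11).

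The cost is one phrase and three short sentences in Section 9, plus the SOFA reconciliation. No patients or visits are added, since ISTH DIC is already scheduled on Day 9. The downsides are that SOFA is no longer available as another basis for the split, and that the coarser DIC score leaves more patients tied. The change does not supply the missing comparison between randomised arms.

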Thus, COVID might be a dysregulated inflammatory state superimposed on disseminated intravascular coagulation (DIC) with consumptive coagulopathy [PMID: 32302438]. These patients are at high risk for both thrombosis and bleeding, as well as an overwhelming cytokine storm. The pathogenic mechanism is not fully elucidated, but the dysregulated coagulation is probably orchestrated by inflammatory cytokines, lymphocyte cell-death, hypoxia, and endothelial damage [PMID: 32558075]. This is a project to develop an entirely novel evidence-based treatment that targets both the coagulopathy and the inflammation.

In 183 consecutive patients with COVID, the overall mortality was 11.5%. On admission, the non-survivors had higher D-dimer and fibrin degradation product (FDP) levels, longer prothrombin time and activated partial thromboplastin time compared to survivors; 71.4% of the deaths and only 0.6% survivors met the criteria of DIC [PMID: 32073213]

In 40 patients with COVID, whole blood thromboelastometry (TEM) was consistent with hypercoagulability characterized by an acceleration of blood clot formation and higher clot strength. This hypercoagulable state persists for at least 5-10 days and was associated with deep vein thrombosis in six patients (15%), thromboembolism in 2 patients (5%), and catheter-related thrombosis in 12 patients (30%). The ICU and the hospital mortality were 10% and 12.5%, respectively. [PMID: 32394236]

In 16 COVID patients, the pro-coagulant TEM profile was characterized by an increased clot strength (CS), platelet contribution to CS, fibrinogen contribution to CS elevated D-dimer levels, and hyperfibrinogenemia. Fibrinogen levels were associated with interleukin-6 values. [PMID: 32302448].

In 24 COVID patients, the R, K, Alpha, and MA TEM parameters were all consistent with hypercoagulability. Platelet count was normal or increased, prothrombin time and activated partial thromboplastin time were near normal. Fibrinogen, D-dimer, C-reactive protein, Factor VIII and von Willebrand factor, protein C were all increased whereas AT3 was decreased [PMID: 32302438]. In 94 patients with COVID vs 40 healthy controls, whereas D-dimer, fibrin/fibrinogen degradation products (FDP), and fibrinogen (FIB) in all SARS-CoV-2 cases were all higher, but AT3 was lower [PMID: 32172226].

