**4) Number of Subjects\***

The study population will be comprised of 75 patients assigned to one of three groups of 25 COVID (+) patients each.

The proportion of subjects with AT3 levels < 100% will be 50/50 randomization of which 25 subjects with AT3 <100% will be standard of care and 25 subjects with AT3<100% will be standard of care with exogenous AT3 supplementation. The third group will be subjects with AT3 levels  $\geq 100\%$ .

- a. 25 patients with endogenous AT3 >100% who receive standard of care only or
- b. 25 patients with endogenous AT3 <100% who receive standard of care only or
- c. 25 patients with endogenous AT3 <100% who receive standard of care plus supplemental AT3.

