**Appendix A**

**ISTH DIC**, the score is increased by 2 points for abnormal baseline D-dimers (fibrin-related marker) and/or abnormal fibrinogen <1.0 gram/L level (1 point). This scoring algorithm was developed by the ISTH Scientific and Standardization Committee (SSC) committee on DIC and published in 2001. The ISTH DIC is a set of objective criteria for the diagnosis and severity of DIC with a score of  $\geq 5$  correlating with overt DIC, whereas < 5 does not rule out DIC but may indicate DIC that is not overt. The score is only appropriate for use in patients with an underlying disorder that is known to be associated with DIC; e.g., sepsis, severe immunological reactions, etc.

The ISTH DIC score is calculated using

- platelet count ( $\geq 100,000 = 0$ ;  $50,000-99,999 = 1$ ;  $< 50,000 = 2$ ),
- fibrinogen level ( $\geq 100 \text{ mg/dL} = 0$ ;  $< 100 \text{ mg/dL} = 1$ ),
- prothrombin time prolongation above upper limit of normal (ULN)
  - ( $< 3 \text{ seconds} = 0$ ,  $3-6 \text{ seconds} = 1$ ,  $> 6 \text{ seconds} = 2$ ),
- and D-dimer ( $< 2 \text{ times ULN} = 0$ ,  $2-4 \text{ times ULN} = 2$ ,  $> 4 \text{ times ULN} = 3$ ).

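### The two-halves split on a coarse integer change score has no cut-point or tie rule, so group membership and p values depend on an unstated choice

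*Combined protocol and SAP*

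**What the plan says.** Section 7 (Study Endpoints) sets the primary endpoint: "The Primary endpoint is change from baseline in the ISTH DIC Score to Day 9". SOFA change is listed there as secondary.

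Section 9 (Statistics) builds its comparison groups from the outcome: "The study population will be stratified into two halves based on the primary outcome of change from baseline SOFA and/or ICH DC". The last abbreviation is not defined and is presumably the ISTH DIC score. The section continues: "Those with the fastest rate of recovery are compared to those with the slowest rate of recovery". These two groups are what the t, Mann-Whitney, chi-square and Fisher tests compare, and the 1:1 propensity matching uses them too. Significance is declared at p < 0.05.

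Appendix A defines the score from four graded items: platelets 0/1/2, fibrinogen 0/1, prothrombin time 0/1/2 and D-dimer 0/2/3. SOFA, the other permitted splitting variable, is also a sum of integers (Section 8): "Each organ system is assigned a point value from 0 (normal) to 4 (high degree of dysfunction/failure".

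No section gives a cut-point, a rule for ties, a choice between the two scores, or a formula for the rate of recovery.

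**The concern.** A median split works cleanly on a continuous measure. On a short integer scale many patients share the same change. If the middle ranks fall inside such a block, equal halves can be formed only by sending patients with identical outcomes to different groups.

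Two analysts who both follow Section 9 could then classify the same patients differently and reach different conclusions at 0.05. A tie rule chosen after the data are seen also leaves room for selective reporting. These are the only group tests Section 9 describes. Cutting the score in two also discards information on the relation the plan wants to show, that of AT3 with recovery.

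**Working it through.** The plan states no power, effect size, SD or distribution of change, so there is no figure of its own to reproduce. The sample is 3 × 25 = 75 (Section 4), and 75 / 2 = 37.5, so the nearest thing to halves is 37 and 38.

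**1. The scale.** The Appendix A maxima sum to 2 + 1 + 2 + 3 = 8. The score takes the integers 0 to 8, and its change takes 17 values, −8 to +8. If only D-dimer moves, change takes 7 values, −3 to +3.

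**2. What the background suggests.** For one cited cohort of 24 patients, Section 2 reports: "Platelet count was normal or increased, prothrombin time and activated partial thromboplastin time were near normal", with fibrinogen raised. At the Appendix A thresholds those three items would mostly score 0 and leave D-dimer as the moving item. In the cited cohort of 183, mortality was 11.5%, and DIC criteria were met by 71.4% of deaths and 0.6% of survivors. The implied share with DIC is 0.115 × 0.714 + 0.885 × 0.006 = 0.087, about 9%. This fits many unchanged scores but does not establish them.

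**3. Is there a tie at the cut?** The share with zero change is not in the documents, so it was varied from 20% to 80% (N = 75, changes −3 to +3, 4,000 simulated trials per setting).
- At 50% to 80% zeros, the cut between ranks 37 and 38 fell in a tied block in practically every trial, always at 0, with about 38 to 60 patients tied.
- At 20% to 40% zeros, it fell in a tied block in 90% to 99.5% of trials, with about 15 to 30 patients tied. The block was not always at 0: with 20% zeros and 50% improved, it was at 0 in 40% of trials.
- For a SOFA-like change (rounded normal, assumed SD 2 to 4), there was a tie at the cut in 87% to 96% of trials, with about 8 to 15 patients tied.

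**4. What if tied patients are kept together?** The groups stop being halves.
- With 50% zeros and 30% improved, the fast group has 75 × 0.30 ≈ 22 patients if ties go to slow, and 75 × 0.80 = 60 if ties go to fast.
- With 70% zeros and 20% improved, the figures are 75 × 0.20 = 15 and 75 × 0.90 ≈ 68.

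**5. Effect on conclusions and power.** D-dimer was simulated as a lognormal multiple of the upper limit of normal (ULN) and scored 0/2/3 at <2, 2–4 and >4. Assumed ranges were baseline median 1.5 to 8 × ULN, geometric SD 2 to 3, and log change to Day 9 with mean −0.2 to −0.5 and SD 0.5 to 0.8. Zero change then occurs in about 51% to 79% of patients. Mid-range inputs are median 3 × ULN, geometric SD 2.5, and log change −0.35 with SD 0.65. With these and n = 75:
- At a correlation of 0.3 between AT3 and the log D-dimer fall, the two cuts that keep ties together (all to slow, all to fast) disagree on significance at 0.05 in about 33% of datasets.
- At correlation 0.5, power is about 42% for halves with random ties, 63% for any fall versus no fall, and 80% for Spearman on the same integer scores. Repeat runs differ by up to about five points and keep this order.
- Type I error is about 5% for both the random-tie split and Spearman. The problem is reproducibility and power, not an inflated error rate.

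**The case against.** Several points on the other side are fair.

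- A reader might infer that the rule cannot be applied at all. It can: a cut at or below the median versus above it runs on any data. What it does not give is the two halves that the plan promises.
- A reader might infer that most changes will be exactly 0. No document says so. It is an inference from Appendix A and one small cohort in Section 2. The same section reports longer prothrombin times in non-survivors, and Section 10 lists low platelets and coagulation dysfunction as expected events. The point does not need this inference, since a tied block at −1 or −2 has the same effect.
- A reader might infer that almost any dataset can be made significant or not by tie-breaking. That impression comes from asking whether any of 100 random tie-breaks falls on each side of 0.05. By that measure about 78% of datasets cross even with no true association. The comparison of the two tie-consistent cuts, about one third, is the fairer measure. Likewise the 42% power assumes random allocation of ties, which the plan does not propose; a fixed cut recovers part of the loss.
- SOFA has a wider scale and smaller tied blocks, and a combined criterion could break some ties. Instability of p values was not computed for SOFA. But the plan does not choose between the scores, which adds a further unstated choice.
- Section 9 also expects AT3 to correlate with recovery and mentions multivariate models, so the split is not the only route to the question. Neither of those is specified well enough to replace it.

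The pilot label does not answer the point, because Section 9 declares significance at a fixed threshold.

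**Conclusion.** The point holds in this form: Section 9 rests its group tests and matching on halves of a coarse integer change, with no cut-point or tie rule, and a tie at the median is very likely under every distribution tried. Equal halves then require an arbitrary choice, and tie-consistent cuts give unequal groups.

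The scale of the score and the absence of a rule come from the documents. The sizes do not: the tie frequencies rest on assumed shares of change, and the one-third disagreement and the power figures rest on assumed D-dimer distributions and AT3 correlations. They are illustrations. The documents do not support saying that the analysis is impossible or that most patients will show no change.

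This should be changed before analysis. It is more than a missing detail, because using the whole score is a better method on the same data. Section 9 also states no comparison of the two randomized arms. That is a separate gap, and repairing the split does not close it.

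**What to change.** Replace the two-halves split with an analysis of the full change in ISTH DIC score from baseline to Day 9. There are two suitable options:
- Proportional-odds regression of the change on baseline AT3, with baseline DIC score and study arm (AT3 supplementation) as covariates.
- A tie-corrected rank correlation of baseline AT3 with the change, done within arm or restricted to patients not given AT3.

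A simple correlation over all 75 should not be used. It would pool in the 25 patients who receive AT3, and they are eligible for it because their baseline AT3 is below 100%. In the regression, code the arm term as supplemented or not, because the third group is itself defined by baseline AT3.

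If a two-group display is wanted, name the score, fix the cut in advance (for example any fall versus no fall) and accept unequal groups.

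The cost is plan wording, with the same data, and loss of the equal-halves presentation. Restricting the correlation to the 25 + 25 = 50 patients not given AT3 lowers power: at correlation 0.5, Spearman falls to about 58% to 61%, still above the 25% to 26% for a random-tie split at that size.

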**ClinicalTrials.gov Identifier**  
**NCT04899232**

**1) Objectives\***

This will be a prospective, randomized, open label, interventional pilot trial to test the hypothesis that deficient endogenous AT3 is associated with a prothrombotic hyperinflammatory state associated with COVID-19.

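### Section 9 plans no comparison of the two randomised arms on the primary endpoint; it compares fast with slow recoverers across the whole study population

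*Combined protocol and SAP*

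**What the plan says.** Section 4 (Number of Subjects) sets up three groups of 25:

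- Group a: AT3 at or above 100%, standard of care, not randomised. (The list in Section 4 writes this as above 100%.)
- Group b: AT3 below 100%, randomised to standard of care.
- Group c: "25 patients with endogenous AT3 <100% who receive standard of care plus supplemental AT3".

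Section 7 (Study Endpoints) states: "The Primary endpoint is change from baseline in the ISTH DIC Score to Day 9". Section 8 (Procedures Involved) has every consented patient scored on the "scale (ISTH DIC) on study visit days 1, 3, 5, 7, 9 and 11", and the Appendix B flowsheet agrees.

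Section 9 (Statistics) opens its analysis with "The study population will be stratified into two halves based on the primary outcome of change from baseline SOFA and/or ICH DC", followed by "Those with the fastest rate of recovery are compared to those with the slowest rate of recovery". Demographic and physiologic variables are then tested between those two halves. Multivariate models follow, judged by area under the ROC curve, sensitivity, specificity and predictive values. Last comes 1:1 nearest-neighbour propensity matching, again of fastest against slowest.

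The only between-group wording we found is in Appendix C, for a secondary endpoint: "Mortality (%) of overall and between groups". It names no test and does not say which groups.

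**The concern.** The randomised contrast, c versus b, is the one comparison in this trial that can support a causal statement about AT3 supplementation. The data for it are scheduled, but the analysis section does not use them. Three consequences follow.

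- **No estimate for the randomised question.** Grouping patients by the outcome and asking what differs between the groups does not give a treatment effect in units of the DIC score.
- **An unplanned comparison later.** Any arm comparison would have to be devised after open-label data had been seen. That includes the choice of baseline adjustment and the handling of deaths and early discharges.
- **A mixture of two kinds of AT3.** Section 9 expects AT3 to correlate with recovery. Across all 75 patients, AT3 after baseline is endogenous in groups a and b but partly infused in group c, so the correlation answers neither the associative question nor the treatment question cleanly.

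Section 9 also misnames the outcome used for the split. ICH DC is probably a slip for ISTH DIC, but the added SOFA and/or is a real conflict, because Section 7 makes SOFA change a secondary endpoint.

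**Working it through.** **Text check.** The documents give no power, SD or effect size, so there is no figure of theirs to reproduce. Each element of Section 9 was checked for a c-versus-b comparison.

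| Element of Section 9 | Groups or predictors named | Arm comparison? |
|---|---|---|
| Main contrast | Fastest v slowest half of the study population | No |
| t test / Mann-Whitney | Demographic and physiologic variables, fastest v slowest | No |
| Chi-square / Fisher | Categorical variables, groups not named; follows the fast/slow sentence | Not stated |
| Multivariate models | No predictor named; prediction metrics | Not stated |
| Propensity matching | Fastest v slowest | No |

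Section 4 defines the study population as 75, so the split includes group a.

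**Counts from the documents.** Non-randomised share of the split: 25/75 = one third. If treatment were tested as a categorical variable between halves, group c (25) would be set against a + b (25 + 25 = 50), of whom 25/50 = half are not randomised.

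**Illustration.** Section 9 does not specify this test, and every input is an assumption: normal scores with SD 1 at each time, 25 per group, complete data, baseline/Day 9 correlation 0.5 (range 0.3 to 0.7), two-sided 5%. The split puts 38 patients in the fast half and 37 in the slow half, with an uncorrected Pearson chi-square of treatment (c v a + b) by half. Results are by simulation.

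| Scenario | Split, correlation 0.5 (0.3 to 0.7) | Arm comparison, c v b |
|---|---|---|
| No AT3 effect; a 0.8 SD better | signals harm in 20% (16 to 31%) | about 5% error, both directions together |
| Effect 0.8 SD; a equally better | detects it in 27% (20 to 38%) | 79% (64 to 95%) unadjusted; 89% (82 to 98%) baseline-adjusted |
| Effect 0.8 SD; a like b | detects it in 74% | 79% unadjusted; 89% adjusted |
| No AT3 effect; a like b | 5% false positives | about 5% error |

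**Precision of the arm comparison, same assumptions at correlation 0.5.** The 95% half-width is t × SD × √(2/25), with √(2/25) = 0.283.

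- Unadjusted change: SD = √(2 × (1 − 0.5)) = 1.0, so 2.011 × 1.0 × 0.283 = 0.57 SD.
- Baseline-adjusted: SD = √(1 − 0.5²) = 0.866, so 2.012 × 0.866 × 0.283 = 0.49 SD.

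**Sensitivity to the odd patient.** With 37 fast and 38 slow, the split's 20%, 27% and 74% become about 27%, 21% and 70%. Keeping 38 fast and adding a continuity correction lowers the two power figures to about 13% (a like c) and 57% (a like b). The direction holds throughout; the exact percentages do not.

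**The case against.** - **The trial is a pilot with an associative aim.** Section 1 sets out to "test the hypothesis that deficient endogenous AT3 is associated with a prothrombotic hyperinflammatory state associated with COVID-19", and a fast/slow comparison could explore that. This is fair as far as it goes. But the same sentence calls the trial randomised and interventional, and Section 2 proposes AT3 as a treatment. A pilot need not be powered, but it should still report an estimate and interval for its randomised contrast.
- **Omission is not exclusion.** An arm term could enter the multivariate models, since no predictors are listed. That is true, but nothing says it will, and the stated metrics measure prediction and not a treatment effect.
- **The simulation measures an analysis the plan does not specify, on a scale that does not fit.** This stands as a limit on the numbers. By Appendix A the ISTH DIC score is an integer from 0 to 8, with D-dimer scoring only 0, 2 or 3, so changes will be tied and a clean 38/37 split may not exist. Deaths and early discharges were also left out. The power and half-width figures are therefore not forecasts.
- **The remedy is more than a change of words in Section 9.** This is partly right. The discharge rule in Section 7 is categorical and has no stated conversion to a score change. Appendix B schedules no blood draw after discharge, so some Day 9 scores will be missing.

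None of these points supplies the missing arm comparison.

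**Conclusion.** The concern holds, with high confidence, and must be fixed. It rests on the text: no part of the plan compares group c with group b on change in ISTH DIC score to Day 9, and the contrast that is named groups patients by outcome. The firm sizes are the counts: 25 of the 75 patients in the split, and 25 of the 50 comparators if treatment were tested between halves, are outside the randomisation.

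The percentages illustrate direction. Pooling group a distorts the treatment contrast if its prognosis differs from group b's. If the prognosis is the same, the split has about the nominal error rate and slightly less power than the unadjusted arm comparison. Even then it gives no effect estimate on the score.

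**What to change.** 1. Make the primary analysis group c versus group b as randomised (25 v 25), on change in ISTH DIC score from baseline to Day 9, adjusted for baseline score, with the estimate and 95% confidence interval. No power claim is needed.
2. Replace the outcome named in Section 9 with the Section 7 endpoint.
3. State how deaths before Day 9 and early discharges enter this analysis. Section 7 now says "Subjects discharged prior to completion of intervention would be classified as having a successful outcome", which does not translate into a score change. Add a sensitivity analysis under an alternative handling.
4. For the associative hypothesis, relate baseline AT3, as a continuous variable, to outcome in the untreated groups a and b only, and label the result observational.
5. Label the fast/slow comparison and the propensity matching exploratory, or drop them.

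Items 1 to 3 are the essential ones; other sound methods could serve for item 4. The cost is a rewrite of Section 9, with a clarifying sentence in Section 7 on discharged patients. The DIC scores are already scheduled in all groups, so no new patients, visits or assays are required.
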